2.8 Safety analyses

In general, for Part 1 safety analyses, the SAF will be used; for Part 2 safety analysis, the OAS will be used.

Safety summaries will include only treatment emergent adverse events (TEAEs) by Part. For Part 1, TEAEs are defined as adverse events (AEs) starting on or after the first dose of doubleblind treatment or AEs that were present prior to start of double-blind treatment but increased in severity in Part 1. For Part 2, TEAEs are defined as AEs starting after the Day 360 dosing time or AEs that were present prior to the Day 360 dosing time but increased in severity in Part 2. For Part 1, if the AE start date is the same as the date of the first dose of double-blind treatment but the time is not available for comparison, the AE will be considered as treatment but the time is not available for comparison, the AE will be considered as treatment but the time is not available for comparison, the AE will be considered as treatment but the time is not available for comparison, the AE will be considered as treatment but the time is not available for comparison, the AE will be considered as treatment but the time is not available for comparison.

Vital signs values that have complete data and time values will be assigned to pre- or post-dose assessment (as per protocol) based on the actual date/time. For values with missing date/time, the scheduled visit date and time will be used. This rule will be applied to data from scheduled visits only. If a measurement scheduled as pre-dose is actually performed post-dose, or vice versa, the data will not be used for visit/time point summary.

2.8.1 Adverse events (AEs)

The number (and percentage) of participants with TEAEs will be summarized by Part in the following ways:

- Overall summary.
- By treatment, primary system organ class (SOC) and preferred term (PT).
- By treatment and PT.
- By treatment and PT for most common TEAEs (For Part 1: occurring in >= 3% of participants in total; for Part 2: threshold to be determined before final database lock).
- By treatment, SOC, PT and maximum severity.
- By treatment, SOC and PT for TEAEs leading to study drug discontinuation.
- By treatment, SOC and PT for TEAEs related to study drug.

The number (and percentage) of participants with treatment emergent serious adverse events (TESAEs) will be summarized by Part, in the following ways:

- By treatment, SOC and PT.
- By treatment and PT.
- By treatment, SOC and PT for TESAEs related to study drug.

Novartis	Confidential	Page 30 of 48
Clinical Study Report Appendix 16.1.9, v1.0		Study No. CKJX839C12301

Novartis	For business use only	Page 29
SAP amendment 4		CKJX839C12301

Unless otherwise specified, SOCs will be sorted alphabetically and, within each SOC, the PTs will be sorted in descending order of frequency in the total column. If a participant reported more than one AE with the same PT, the AE will be counted only once. A participant with multiple AEs within a SOC is only counted once towards the total of the SOC. In case of summary by severity or relationship to study drug, summary will be done using the most severe or related occurrence respectively. Listing of all AEs and SAEs will be provided.

AE reporting for CT.gov and EudraCT

For the legal requirements of clinicaltrials.gov and EudraCT, two required tables on TEAEs which are not SAEs with an incidence greater than X% (X will be selected prior to final database lock) and on TESAEs and TESAEs suspected to be related to study treatment will be provided by system organ class and preferred term on the Safety Set population.

If for a same patient, several consecutive AEs (irrespective of study treatment causality, seriousness, and severity) occurred with the same SOC and PT:

- a single occurrence will be counted if there is ≤ 1 day gap between the end date of the preceding AE and the start date of the consecutive AE.
- more than one occurrence will be counted if there is > 1 day gap between the end date of the preceding AE and the start date of the consecutive AE.

For occurrence, the presence of at least one SAE / SAE suspected to be related to study treatment / non-SAE has to be checked in a block e.g., among AEs in $a \le 1$ day gap block, if at least one SAE is occurring, then one occurrence is calculated for that SAE.

The number of deaths resulting from SAEs suspected to be related to study treatment and SAEs irrespective of study treatment relationship will be provided by SOC and PT.

These summaries will be provided after full study completion.

Injection site reactions

The number and percentage of participants who reported injection site reaction TEAEs will be summarized in the following ways:

- SOC, PT, treatment group and Part.
- SOC, PT, severity, treatment group and Part.

Listing will be provided for participants with injection site reactions.

The time to the first injection site reaction will also be summarized by treatment and Part using the following categories: \leq 4h, 4h to \leq 12h, >12h. The time (hours) to the event will be calculated from the most recent administration of study drug. The duration of the first and the longest injection site reaction will be summarized by treatment and Part using descriptive statistics. The outcome of the first and the longest injection site reaction will be summarized using the following categories: Resolved (\leq 4h, >4h to \leq 7 days, >7 days to \leq 14 days, >14 days), not resolved and unknown. The total number of injection site reactions per participant will be summarized in categories (e.g., 1, 2, 3, and >3 etc.). Symptoms of injection site reactions will be summarized by treatment group and Part.

Novartis	For business use only	Page 30
SAP amendment 4		CKJX839C12301

Other safety topics

The number and percentage of participants who reported TEAEs of other safety topics will be summarized by PT, treatment group and Part. PTs will be sorted in descending order of frequency in the total column. If a participant reported more than one AE with the same PT, the AE will be counted only once. If a participant reported more than one AE within the same safety topic, the participant will be counted only once at that safety topic. Listing of participants with AEs of other safety topics will be provided.

The Compound Case Retrieval Strategy (CRS) will be used to determine the MedDRA search criteria to be used to identify events of other safety topics.

AEs of other safety topics will include the following:

- Hepatic events
- Renal events
- Hypersensitivity events
- Neurological events
- Psychiatric events
- Musculoskeletal events
- Cardiac events
- New onset diabetes and worsening of glycemic control

For search criteria of AE of other safety topics, refer to Appendix 5.4.

For detailed analysis of new onset diabetes and worsening of glycemic control, please see Section 2.8.4.

Any immune-related events will be identified in the SOC of immune system disorders.

The percentage of participants with abnormal ECG findings reported as AEs will be summarized by treatment group and Part.

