4.5 Risks and benefits

It is widely recognized that LDL-C plays a major role in the initiation and progression of ASCVD, including in HeFH, and accumulated exposure of elevated LDL-C is causally related to the development of ASCVD. As the degree and duration of exposure to elevated LDL-C levels increases the atherosclerotic burden, early treatment of HeFH is vital. Published expert guidelines recommend a LDL-C target of \leq 130 mg/dL in children/adolescents. Current treatment options to achieve these targets are still limited for children with FH and the well-known limitations of contemporary therapies are particularly relevant among pediatric patients with FH.

In adult studies in participants with ASCVD, ASCVD risk equivalents, and/or HeFH, inclisiran given on Day 1, Day 90 and every 6 month thereafter lowered LDL-C by \sim 50% versus placebo in participants on maximally tolerated statin therapy \pm other lipid-lowering therapies. The effect was persistent over time and reversible on stopping inclisiran.

In non-clinical toxicity studies, inclisiran was not carcinogenic or genotoxic, there was no effect on paternal performance, spermatogenesis, estrous cycle, and uterine or ovarian parameters and inclisiran did not show evidence of embryolethality, fetotoxicity, or teratogenicity. In addition, there were no effects of inclisiran on the development of the F1 generation, including survival, growth, physical and reflexological development, behavior, and reproductive performance. The safety profile of inclisiran in clinical studies was generally comparable to placebo. The only Adverse drug reaction (ADR) identified in clinical studies was a higher incidence of TEAEs at the injection site with inclisiran (preferred terms of injection site erythema, injection site hypersensitivity, injection site pruritus, injection site rash, and injection site reaction). However, all TEAEs at the injection site were localized, were predominantly mild or occasionally moderate, transient, and resolved without sequelae. The impact of this side effect is further mitigated by the infrequent dosing regimen of inclisiran.

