6.1.1 Investigational and control drugs

The sponsor will provide the following investigational and control drugs as single-use pre-filled syringes for s.c. injection (Table 6-1).

Part 1 (Year 1) including "Switch" Day 360:

- Inclisiran sodium 300 mg (equivalent to 284 mg inclisiran) in 1.5 mL solution
- Placebo formulation to this active drug formulation

Placebo will be supplied as sterile normal saline (0.9% sodium chloride in water for injection). Placebo will be administered as a 1.5 mL s.c. injection to match the dose in the inclisiran arm.

The placebo pre-filled syringes will be blinded and look identical to the corresponding inclisiran pre-filled syringes.

Part 2 (Year 2):

• Inclisiran sodium 300 mg (equivalent to 284 mg inclisiran) in 1.5 mL solution

Table 6-1	Investigational and control drug
	inteenganena and eender arag

Investigational/ Control Drug	Pharmaceutical Dosage Form	Route of Administration	Supply Type	Sponsor (global or local)
Inclisiran sodium 300 mg (equivalent to 284 mg inclisiran [*]) in 1.5 mL solution	Solution for injection	Subcutaneous injection	Solution for injection in pre-filled syringe	Sponsor (global)
Placebo	Solution for injection	Subcutaneous injection	Solution for injection in pre-filled syringe	Sponsor (global)
* Inclisiran is also referred to as KJX839				

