1.1 Study design

This study is a two-part (double-blind, placebo-controlled / open-label) multicenter study in adolescents (aged 12 to <18 years) with HeFH and elevated LDL-C (>130 mg/dL / 3.4 mmol/L) on stable, individualized, optimal SoC background lipid-lowering therapy (including maximally tolerated statin treatment). The overall study duration is 748 days.

Following an approximately 4 weeks screening/run-in period, the study has two sequential parts (Figure 1-1).

- **Part 1 (Year 1):** 12 months double-blind, parallel group period in which participants will be randomized to receive either inclisiran sodium 300 mg (equivalent to 284 mg inclisiran) s.c. or placebo (given at Days 1, 90 and 270).
- **Part 2 (Year 2):** 12 months single arm, open-label follow-up period with all participants receiving inclisiran sodium 300 mg s.c. Participants randomized to placebo in Part 1 will receive inclisiran starting on Day 360 ("Switch" Day 360). Participants randomized to inclisiran in Part 1 will receive placebo on Day 360. This dose of inclisiran/placebo on Day 360 will remain blinded in order to maintain the blind for Part 1 of the study. All participants will receive subsequent doses of open-label inclisiran on Days 450 and 630.

A minimum of 102 participants (actual enrolled number of participants: 141), who meet the inclusion/exclusion criteria were to be randomized in a 2:1 ratio to receive either inclisiran sodium 300 mg s.c. or placebo on Day 1 (baseline). Detailed information regarding sample size calculation is provided in Section 3.

Randomization was stratified by age group (≥ 12 to <15 years and ≥ 15 to <18 years) to include a minimum of 40 participants in each of the two age strata.

* Primary endpoint assessed at Day 330. # "Switch Day": Participants randomized to placebo in Part 1 will start to receive inclisiran on Day 360. Participants randomized to inclisiran in Part 1 will receive placebo on Day 360 only to maintain the blind for Part 1.

The primary endpoint will be measured at Day 330.

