2.1 Data analysis general information

All analyses will be performed by Novartis. The most recent version of SAS available in the statistical programming environment of Novartis will be used for the analysis.

Part 1 data are defined as all data collected starting from the screening visit up to the day 360 visit date prior to dosing on this day/date. Part 1 data will be presented by two separate groups (inclisiran and placebo). The total column will be presented in all outputs of Part 1 as needed and will be specified in TFL shell document.

Part 2 data analysis will include all data collected starting from after dosing on day 360. Part 2 data will be presented in two separate groups, (1) inclisiran since Day 1 and (2) placebo-to-inclisiran, unless otherwise specified. The column labels for these two groups will be inclisiran-inclisiran and placebo-inclisiran. The total column will be presented in all outputs of Part 2 as needed and will be specified in TFL shell document.

For instances, where it will not be possible to distinguish whether data belong to Part 1 or Part 2, based on the dosing time on the day 360 visit, all data collected from screening up to the day 360 visit will be considered as Part 1 data and all data captured after the day 360 visit (starting from day 360 visit + 1 day) will be considered as Part 2.

Part 1 data analysis will be performed after all participants completed the day 360 visit (Part 1) or discontinued the study prior to the Day 360 visit. For each participant, data collected in the database till the end of study Part 1 (up-to Day 360 visit as mentioned above) will be included in this analysis. Hence the Day 360 visit of a participant will serve as data cut-off date for that participant. All events with start date before or on the cut-off date and for which the end date has not been reached yet or they are ongoing at final visit will be reported as 'ongoing'. The same rule will be applied to events starting before or on the cut-off date and not having a documented end date. The assessment of study primary objective and key secondary objectives will be based on this analysis.

Part 2 data analysis will be conducted after all participants either completed the study or discontinued early.

Both Part 1 and Part 2 analyses will be reported in the CSR. For summary of the analyses that will be performed for Part 1 analysis and Part 2 analysis see Appendix 5.3.

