2.2 Analysis sets

The Screened Set (SCR) includes all participants who provided study informed consent.

The Randomized Set (RAN) consists of all participants who received a randomization number, regardless of whether double blind treatment received or not.

The Full Analysis Set (FAS) consists of all randomized participants with the exception of those mis-randomized participants who did not receive study drug. Mis-randomized participants are defined as not qualified for randomization and were inadvertently randomized into the study. According to the intent to treat principle, participants will be analyzed according to the treatment they have been assigned to during the randomization procedure. The FAS will be used in analyses for the primary, secondary, and the study objectives in Part 1.

The Safety Set (SAF) includes all participants who received at least one dose of study treatment. Participants will be analyzed according to the study treatment received. This will be the primary population for the safety analyses in Part 1.

Novartis	For business use only	Page 20
SAP amendment 4		CKJX839C12301

Note that the Safety Set allows the inclusion of non-randomized participants who receive double-blind treatment in error.

The Open-label Phase Analysis Set (OAS) includes all participants who entered study Part 2 and received at least one dose of study drug in Part 2. The OAS will be used to analyze the data from participants who entered Part 2.

Note that in Part 1 the number of participants in FAS equals the number of participants in SAF, so only one open-label phase analysis set is defined for Part 2.

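### Part 2 injection-site reaction tables set one saline plus two active injections against three active injections, and no planned summary separates them

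*SAP*

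**What the plan says.** **Injections in Part 2.** SAP 1.1 sets out the Day 360 switch: "Participants randomized to inclisiran in Part 1 will receive placebo on Day 360", and "Participants randomized to placebo in Part 1 will receive inclisiran starting on Day 360". It continues: "All participants will receive subsequent doses of open-label inclisiran on Days 450 and 630". Protocol 6.1.1 identifies the placebo as normal saline.

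**Start of Part 2.** SAP 2.1 starts Part 2 data after dosing on Day 360. SAP 2.8 starts Part 2 treatment-emergent events at the same point. If dosing time cannot separate the Parts, the SAP 2.1 fallback assigns everything up to and including the Day 360 visit to Part 1.

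**Columns.** SAP 2.1: "Part 2 data will be presented in two separate groups, (1) inclisiran since Day 1 and (2) placebo-to-inclisiran, unless otherwise specified". The labels are inclisiran-inclisiran and placebo-inclisiran.

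**ISR tables.** SAP 2.8.1: "The number and percentage of participants who reported injection site reaction TEAEs will be summarized in the following ways". Incidence and severity are then grouped by treatment group and Part. Time to first ISR, duration and symptoms follow the same grouping, and outcome has no finer one. Onset is timed from the last injection of study drug, a term that Protocol 6.6.1 uses for both inclisiran and placebo.

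**Dosing tables.** SAP 2.4.1 summarises the number of doses by treatment group and Part without saying whether saline counts. It also summarises participants dosed by study visit.

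**The concern.** Injection-site events are the one drug reaction the protocol recognises. Protocol 4.5: "The only Adverse drug reaction (ADR) identified in clinical studies was a higher incidence of TEAEs at the injection site with inclisiran". Part 2 is there to add longer-term safety data on inclisiran, so its ISR table will be read closely.

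The two columns of that table do not rest on the same number of active injections, and their labels do not show it. A lower ISR percentage in inclisiran-inclisiran could be read as better local tolerability with continued use when it reflects only one fewer active injection. The summaries of the first ISR are the most exposed, because the first Part 2 injection is saline in one column and active drug in the other.

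The SAP 2.1 fallback adds a second route to error. A participant in the placebo arm who reacts to the Day 360 inclisiran, but whose event cannot be placed by dosing time, would be counted in Part 1 under placebo.

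**Working it through.** The plan gives no ISR rate and no figure to reproduce. The check is a count of injections followed by an illustration under stated assumptions.

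**Step 1: injections per participant on the full schedule (SAP 1.1)**

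| Column | Day 360 | Day 450 | Day 630 | Active | Saline |
|---|---|---|---|---|---|
| inclisiran-inclisiran | saline | inclisiran | inclisiran | 2 | 1 |
| placebo-inclisiran | inclisiran | inclisiran | inclisiran | 3 | 0 |

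SAP 1.1 gives 141 enrolled and 2:1 allocation. The documents give no arm sizes. An exact split with no dropout and no withheld doses (assumption) would be 94 and 47. Then 94 of 94 × 3 = 282 Part 2 injections in inclisiran-inclisiran are saline (33%), against none of 47 × 3 = 141 in the other column.

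**Step 2: expected percentage with at least one Part 2 ISR**

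Let p be the ISR risk per active injection, the same in both columns, and q the risk per saline injection, with injections independent. Both values are assumptions.

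- inclisiran-inclisiran: 1 − (1 − p)² × (1 − q)
- placebo-inclisiran: 1 − (1 − p)³

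At p = 5% and q = 1%:

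- 1 − 0.95² × 0.99 = 1 − 0.8935 = 10.65%
- 1 − 0.95³ = 1 − 0.8574 = 14.26%
- gap: 3.6 percentage points with no difference in active risk

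**Step 3: range**

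| p | incl-incl, q = 0% | q = 1% | q = 2% | placebo-incl | Gap, q = 0% to q = 2% (points) |
|---|---|---|---|---|---|
| 2% | 4.0% | 4.9% | 5.9% | 5.9% | 1.9 to 0.0 |
| 5% | 9.8% | 10.7% | 11.6% | 14.3% | 4.5 to 2.7 |
| 10% | 19.0% | 19.8% | 20.6% | 27.1% | 8.1 to 6.5 |
| 20% | 36.0% | 36.6% | 37.3% | 48.8% | 12.8 to 11.5 |

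The gap is zero where saline and active risks are equal, and reaches about 13 points at the top of the range.

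**Step 4: effect on the summaries of the first ISR**

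The saline comes first, so the share of inclisiran-inclisiran participants with an ISR whose first one followed saline is q / [1 − (1 − p)²(1 − q)]. At p = 5% and q = 1% this is 0.01 / 0.1065 = 9.4%.

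**Step 5: what a correction must do**

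Taking only the saline reactions out of the column leaves 1 − 0.95² = 9.75% against 14.26%, a gap of 4.5 points instead of 3.6. Relabelling alone therefore makes the contrast worse. Restricting both columns to Days 450 and 630 gives two active injections in each, and an expected 9.75% in both at p = 5%.

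**The case against.** The strongest reply is that the design is disclosed and the tables carry little inferential weight. The SAP states the Day 360 placebo openly. Part 2 is single-arm, open-label and descriptive, with no test between columns. The controlled ISR evidence comes from Part 1, reported separately. ISRs are also listed by participant, and the table shells, which are not among the documents, might contain a split or footnote. All of this stands and limits the consequence. It does not supply the missing rule: nothing in the SAP attributes a Part 2 ISR to the product injected, and a listing does not correct a summary table.

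A reader might go further in four ways that the documents do not support.

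- *That saline is classed as inclisiran.* The column label names a treatment sequence, and no text reclassifies the saline dose.
- *That the dosing summaries hide the saline.* Participants dosed are summarised by visit (SAP 2.4.1; Protocol 12.3 likewise), which isolates Day 360. Only the dose count by Part is unclear.
- *That the open-label analysis set is wrongly defined.* It "includes all participants who entered study Part 2 and received at least one dose of study drug in Part 2", so a participant whose only Part 2 injection was saline appears to qualify. In the inclisiran arm that participant was scheduled for inclisiran on Days 1, 90 and 270, and Protocol 4.2 describes an effect lasting beyond six months after one dose. Inclusion is not shown to be an error.
- *That the plan reports a biased rate per injection.* No such rate is planned; SAP 2.8.1 counts participants, and reactions per participant.

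It is also fair to say that the gap comes mainly from two versus three active injections, not from the saline reactions themselves, as Step 5 shows. The fix must therefore match denominators and not merely relabel.

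**Conclusion.** The point holds as a reporting defect in the Part 2 ISR summaries. Followed as written, the plan gives ISR percentages based on two active injections plus one saline in one column and three active in the other. They cannot be compared without allowing for that difference.

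The injection counts follow directly from the schedule. The size does not: every ISR risk used here is an assumption, as are independence between injections and equal active risk in both columns. On those terms the dosing pattern alone produces a gap of 0 to about 13 percentage points, with 10.7% versus 14.3% as the central illustration.

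To call the columns not comparable at all would be too strong, because Days 450 and 630 are active in both. Even there the columns differ in earlier inclisiran exposure, so that contrast remains descriptive. The efficacy analyses and the Part 1 comparison are untouched, apart from Day 360 events that the SAP 2.1 fallback might move into Part 1.

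**What to change.** 1. **SAP 2.8.1.** Add a Part 2 ISR summary by injection visit and product last injected: Day 360 saline, Day 360 inclisiran, and Days 450/630 inclisiran. Use the number of participants injected as the denominator for each. Take the product from the recorded dosing and kit data, not from the assigned sequence.
2. **Same section.** Make any comparison between the two Part 2 columns on Days 450 and 630 only.
3. **SAP 2.1 or 2.8.1.** Assign an ISR arising from the Day 360 injection to that injection even when the dosing time is missing, so the fallback cannot place a reaction to active drug in the Part 1 placebo column. Any Part 1 ISR table already produced would need a check for such events.
4. **SAP 2.4.1.** Report active and saline doses separately in the Part 2 dose count.

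The cost is one derived variable, one extra table and a few lines of SAP wording. Protocol 6.7.2 already requires injections to be recorded on the eCRF and kits in the IRT, so no new data are needed and nothing about dosing changes.
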